3.6.3 Plasma Pharmacokinetics

Non-compartmental pharmacokinetic analysis of ISIS 814907 will be carried out on each individual patient data set using Phoenix WinNonlin version 6.3 or higher (Pharsight Corporation, Mountain View, CA). Plasma pharmacokinetic parameters in each patient (when applicable) will be determined. For calculation of PK parameters, all BLQ values will be set to zero. The following plasma PK parameters will be calculated (when applicable) and based on actual sampling times:

Table 2: Plasma PK parameters in Part 1-MAD and Part 2-LTE

| Day 1 X X X Irs post X ys), s the first- This is ree data etermination by ed by X A X X X X X X X X X X X | X |
|---|--|
| X X Irs post X ys), s the first- This is ree data etermination by ed by X | X |
| x x ys), | X X X X |
| ys), s the first- This is ree data etermination by ed by X | X X X |
| s the first- This is ree data etermination by ed by X | X |
| This is ree data etermination by X | X |
| ed by X | |
| | X |
| he dose | X |
| | |
| | |
| Day 1 | D33 |
| X | X |
| X | X |
| X | X |
| ırs post X | X |
| ys), | X |
| s the first- This is ree data etermination | X |
| by | X |
| ed by X | |
| he dose | X |
| 1 | X Irs post X Irs |

Plasma pharmacokinetic parameters (if applicable) will be summarized using descriptive statistics (n, mean, SD, %CV, geometric mean, geometric %CV, median, minimum, and maximum) treatment cohort, nominal dose, and day.

Other PK parameters, as appropriate, may be determined or calculated at the discretion of the PK scientist.

3.7 Pharmacodynamic and Exploratory Analysis

The pharmacodynamic and exploratory analyses, including evaluation of target engagement (total tau and phosphor-tau), will be conducted on the ITT population for the MAD, LTE, and MAD+LTE (where indicated) Periods.

Exploratory analyses of covariates of interest may be performed as post hoc analysis to evaluate their association with changes from baseline in neuroimaging parameters, cognitive assessments, or PK/PD and safety parameters. Covariates of interest may include, but are not limited to, demographics, medical history, concomitant medications, baseline characteristics (i.e., biomarkers, cognitive assessments, genotype and neuroimaging parameters).

3.7.1 Biochemical Analysis

Total tau in CSF is the key exploratory endpoint for the study. Other potential CSF biomarkers included in the analysis are target engagement (phospho-tau), A-beta42, A-beta40, total tau to A-beta42 ratio, A-beta42 to A-beta40 ratio, NfL, total NfH, neurogranin, YKL-40. If total tau to A-beta42 ratio is missing, but total tau and A-beta42 are available, then total tau to A-beta42 ratio will be derived as total tau divided by A-beta42. A-beta42 to A-beta40 ratio will be derived as A-beta42 divided by A-beta40.

In the MAD Period, the actual values, change, and percent change from baseline for CSF biomarkers at each visit will be summarized using descriptive statistics. CSF biomarkers at Day 1 (pre-dose) visit in the LTE will also be added in the MAD Period analysis. The absolute change and percent change from baseline for CSF biomarkers at each post-baseline visit will be compared between ISIS814907-treated groups and the pooled placebo group. The absolute changes from baseline at each post-baseline visit will be compared between each ISIS 814907 treated analysis group and pooled placebo using the ANCOVA with baseline value as covariate or Wilcoxon Rank Sum test, as appropriate. Since the percent change from baseline for biochemical data is not always normally distributed, an analysis of covariance (ANCOVA) model will be fit to the log-transformed data with treatment group as factors and log-transformed baseline value as covariate. The log-transformed data is obtained by taking the log of the ratio of post-baseline and baseline values, i.e., log (Y/X), where Y is the post-baseline value and X is the baseline value of biomarker. The model will provide an estimate of the log ratio \hat{c} , which will be converted back to the ratio scale. The percent change from baseline will then be estimated based

on the estimated ratio scale, that is $[\exp(\hat{c}) - 1] \times 100\%$. The results provide an overall estimate, with corresponding CIs and p-value.

The key analysis in the MAD, Part 1, of the study is the correlation of CSF trough concentration of ISIS 814907 on Day 85 with change in CSF tau concentration from baseline to final CSF collection. ISIS 814907 dose and PK (CSF trough concentration of ISIS 814907 on Day 85) will be related to target engagement using the change in CSF total tau level from baseline to Day 85 and to each CSF collection in the Post-Treatment Period. In the LTE, Part 2, of the study a key analysis will be the correlation of CSF trough concentrations of ISIS 814907 on Day 337 with change in CSF tau concentration from baseline to final CSF collection. Additional correlations between ISIS 814907 dose or PK (CSF trough concentration of ISIS 814907 on Day 85) and changes in pharmacodynamic endpoints may be produced.

In the LTE and MAD+LTE Periods, the actual values, change, and percent change from baseline for CSF biomarkers at each visit will be summarized using descriptive statistics.

Pearson correlation coefficients and related p-value will be reported in the correlation analysis. A scatterplot will be produced to display the correlation between two quantitative variables.

All evaluated parameters will be presented in data listings.

3.7.2 Neuroimaging Analysis

All MRI and PET imaging parameters will be presented in data listings for the MAD and MAD+LTE Periods, separately.

3.7.2.1 Structural MRI – Volumetric Analysis

Structural MRI analyses will be performed for the MAD, LTE, and MAD+LTE Periods.

Hippocampal volumes (left, right and total), whole brain volume, ventricular volumes (including lateral ventricle right, lateral ventricle left, 3rd ventricle, 4th ventricle, all ventricles), and baseline/screening total intracranial volume (ICV) will be assessed using MRI. The ROIs are listed in Appendix Table A1. The volumes of hippocampus, whole brain, and ventricles as a % of total intracranial volume can be calculated by: (Volume / ICV) *100. It is important to note that changes in volume may be due to atrophy or the reduction of tau neurofibrillary tangles, amyloid-beta plaques, or inflammation due to treatment (pseudo-atrophy). Volumetric analyses cannot distinguish between these possibilities.

In the MAD Period, the following results at each visit will be summarized using descriptive statistics:

- Raw results in baseline/screening Total Intracranial Volume (ICV)
- Raw results and absolute changes from baseline in whole brain volume, whole brain volume as a % of total ICV, hippocampal volumes (left, right and total), and hippocampal volumes as a % of total ICV, ventricular volumes (lateral ventricle right,

lateral ventricle left, 3rd ventricle, 4th ventricle, all ventricles), and ventricular volumes as a % of total ICV

The absolute change from baseline in whole brain volume, hippocampal volumes, ventricular volumes as listed in Table A1, and the aforementioned volumes as % of ICV will be compared between each ISIS 814907 treated analysis group and pooled placebo using the ANCOVA with baseline value and baseline age as covariates or Wilcoxon Rank Sum test, as appropriate.

In the LTE and MAD+LTE Periods, the actual values in baseline/screening ICV; the actual values and absolute changes from baseline in whole brain volume, hippocampal volumes, ventricular volumes and the aforementioned volumes as a % of total ICV will be summarized at each visit using descriptive statistics.

3.7.2.2 Exploratory MRI Analyses

3.7.2.2.1 Perfusion Analysis – Arterial spin labelling (ASL)

ASL MRI will be used to quantitate changes in tissue perfusion. The measurement of cerebral blood flow (CBF) in specific regions of interest will assess if changes have occurred between baseline and subsequent imaging timepoints. We will calculate six composites: frontal, cingulate, medial temporal, temporal, parietal, and occipital. Each composite can be derived by averaging the perfusion results from the individual regions listed in Appendix Table A2 constituting the composite.

In the MAD Period, the actual values of each composite and absolute changes from baseline at Day 169 visit will be summarized using descriptive statistics. The absolute changes from baseline at Day 169 will be compared between each ISIS 814907 treated analysis group and pooled placebo using the ANCOVA with baseline value and baseline age as covariates or Wilcoxon Rank Sum test, as appropriate. In case of very few evaluable scans, only descriptive summary by visit will be provided and ANCOVA may not be performed.

In the LTE and MAD+LTE Periods, the actual values and changes from baseline at Day 449 visit will be summarized using descriptive statistics.

3.7.2.2.2 Diffusion Analysis

To assess if the integrity of white matter (WM) is affected by the intervention, analysis of DTI scans will be performed. DTI allows for the identification of microscopic changes in WM tracts (e.g., demyelination) through assessing microscopic changes in water molecule mobility (diffusion). Measurements of water diffusion in WM includes mean, radial, and axial diffusivity and fractional anisotropy (FA). These measurements will be carried out within specific ROIs of the brain. The ROIs include cingulum and hippocampus left and right, forceps major (posterior forceps) and fornix as listed in Appendix Table A3.

In the MAD Period, the actual values and absolute changes from baseline at Day 169 visit will be summarized using descriptive statistics. The absolute changes from baseline at Day 169 will be compared between each ISIS 814907 treated analysis group and pooled placebo using the ANCOVA with baseline value and baseline age as covariates or Wilcoxon Rank Sum test, as appropriate.

In the LTE and MAD+LTE Periods, the actual values and changes from baseline at Day 449 visit will be summarized using descriptive statistics.

3.7.2.2.3 Cortical Thickness

To assess if the intervention is affecting atrophy, the average cortical thickness will be measured in regions known to be affected by AD. T1 MRI scans will be analyzed to determine average cortical thickness (mm) for the whole brain for each patient and timepoint to assess changes with treatment and time. It is important to note that changes in cortical thickness may be due to atrophy or the reduction of tau neurofibrillary tangles, amyloid-beta plaques, or inflammation due to treatment (pseudo-atrophy). Cortical thickness analyses cannot distinguish between these possibilities.

In the MAD Period, the actual values of cortical thickness and absolute changes from baseline at Day 169 visit will be summarized using descriptive statistics. The absolute changes from baseline at Day 169 will be compared between each ISIS 814907 treated analysis group and pooled placebo using the ANCOVA with baseline value and baseline age as covariates or Wilcoxon Rank Sum test, as appropriate.

In the LTE and MAD+LTE Periods, the actual values and changes from baseline at Day 449 visit will be summarized using descriptive statistics.

3.7.2.2.4 White matter lesion analysis

WM lesion analysis will measure the volume of white matter lesions relative to treatment and timepoint. A Lesion Prediction Algorithm (LPA) (Schmit P., 2016) will be implemented to estimate the white matter lesion (WML) volume.

In the MAD Period, the actual values of WML volume and absolute changes from baseline at Day 169 visit will be summarized using descriptive statistics. The absolute changes from baseline at Day 169 will be compared between each ISIS 814907 treated analysis group and pooled placebo using the ANCOVA with baseline value and baseline age as covariates or Wilcoxon Rank Sum test, as appropriate.

In the LTE and MAD+LTE Periods, the actual values and changes from baseline at Day 449 visit will be summarized using descriptive statistics.

3.7.2.2.5 CSF space analysis

The CSF space in individuals will be assessed on T1 and T2 MRI of the brain and spinal cord at screening only. Total CSF space varies between individuals, and atrophy further increases the variability. Assessment of CSF will be determined for each patient on screening MRIs (Chazen et. al, 2017; De Leener et. al, 2018; Sandhya et. al, 2017). Total CSF includes both cranial CSF and spinal CSF. Thus, the total CSF volume is calculated by adding the cranial and spinal CSF volumes. The imaging of CSF space at Screening will be summarized as baseline characteristics.

3.7.2.3 Positron emission tomography (PET) Analysis

This analysis will be performed on the ITT population for the MAD, LTE, and MAD+LTE Periods.

Patients will undergo FDG-PET or Tau-PET imaging to visualize brain changes. In the MAD Period, PET imaging will only be done in Cohorts C and D, and in the LTE, PET imaging will be done in all patients.

- For Cohorts C and D, PET imaging will be done 3 times over the course of the study: during the MAD screening window, at the MAD Day 169 visit, and at the Day 449 visit in the LTE.
- For patients from Cohorts A and B returning to participate in the LTE, PET imaging will be at 2 time points, during the LTE Registration Period and at the Day 449 visit in the LTE.

If Tau-PET is either not available at the site or has not yet been approved, then FDG-PET should be performed. If Tau-PET becomes available to patients in Cohorts C and D in the MAD, then patients should switch to Tau-PET if there are at least 2 imaging time points remaining to enable longitudinal analyses.

Standard uptake values (SUVs) will be extracted to calculate standard uptake value ratio (SUVR), the ratio of target region SUV to reference region SUVs. SUVR values will be computed for the target ROIs. The SUVR values of ROIs will be used to calculate six composites for FDG- or Tau-PET: frontal, cingulate, medial temporal, temporal, parietal, and occipital. Each composite can be derived by averaging the SUVR values from the individual regions listed in Appendix Table A2 constituting the composite. For Tau-PET, the composites will be obtained using the SUVRs that are calculated using cerebellum ventral as the reference region. For FDG-PET, the composites will be obtained using the SUVRs that are calculated using whole cortex, pons vermis and AD preserved as reference regions, respectively.

In the MAD Period, the actual values of each composite and absolute changes from baseline at Day 169 visit will be summarized using descriptive statistics. The absolute changes from baseline at Day 169 will be compared between each ISIS 814907 treated analysis group and pooled placebo using the using the ANCOVA with baseline value as a covariate or Wilcoxon Rank Sum test, as appropriate. In case of very few evaluable scans, only descriptive summary by visit will be provided and ANCOVA may not be performed.

In the LTE Period and MAD+LTE Period, the actual values of each composite and changes from baseline at post-baseline visit will be summarized using descriptive statistics.

FDG- and Tau- PET SUVR results of the target ROIs and the composite values will be presented in data listings for the MAD and MAD+LTE Periods.

3.7.3 Clinical Evaluations

3.7.3.1 Functional Activities Questionnaire (FAQ)

FAQ is used to measure functioning/ability to perform activities of daily living.

In the MAD Period, FAQ total score (actual value, absolute change and percent change from baseline) will be summarized by treatment group and each post-baseline visit at Day 113, 169 and 253 visits using descriptive statistics. The absolute changes from baseline at each post-baseline visit will be compared between each ISIS 814907 treated analysis group and pooled placebo using the ANCOVA with baseline value as a covariate or Wilcoxon Rank Sum test, as appropriate.

In the LTE Period, the actual values, changes and percent changes from baseline at Day 449 visit will be summarized using descriptive statistics.

All FAQ collected scores will be presented in data listings for the MAD and MAD+LTE Periods.

3.7.3.2 Repeatable Battery for the Assessment of Neuropsychological Status (RBANS)

The RBANS assessment yields five index scores, one for each of the domains tested: attention, visuospatial/constructional abilities, language, immediate memory and delayed memory.

In the MAD Period, RBANS index scores, sum of index scores and total scale (actual value, absolute change and percent change from baseline) will be summarized by treatment group and each post-baseline visit at Day 56, 113, 169 and 253 visits using descriptive statistics. The absolute changes from baseline at each post-baseline visit will be compared between each ISIS 814907 treated analysis group and pooled placebo using the ANCOVA with baseline value as a covariate or Wilcoxon Rank Sum test, as appropriate.

In the LTE Period and the MAD + LTE Periods, the actual values, changes and percent changes will be summarized by analysis group and each post-baseline visit within the Period.

All RBANS collected scores will be presented in data listings for the MAD and MAD+LTE Periods.

3.7.3.3 Mini-mental State Examination (MMSE)

The MMSE has five different domains:

- Orientation: a maximum of 10 points, calculated by adding Orientation to Time and Orientation to Place;
- Memory: a maximum of 6 points, calculated by adding Recall and Registration;

- Attention/Calculation: a maximum of 5 points;
- Language: a maximum of 8 points, calculated by adding Naming, Comprehension,
 Repetition, Reading and Writing;
- Visual construction: a maximum of 1 point, which is Drawing.

In the MAD Period, MMSE domain scores and total score (actual value, absolute change and percent change from baseline) will be summarized by treatment group and each post-baseline visit at Day 56, 113, 169 and 253 visits using descriptive statistics. The absolute changes from baseline at each post-baseline visit will be compared between each ISIS 814907 treated analysis group and pooled placebo using the ANCOVA with baseline value as a covariate or Wilcoxon Rank Sum test, as appropriate.

In the LTE and MAD+LTE Periods, the actual results, changes and percent changes will be summarized by analysis group and each post-baseline visit within the period.

All MMSE collected scores will be presented in data listings for the MAD and MAD+LTE Periods.

3.7.3.4 Neuropsychiatric Inventory - Questionnaire (NPI-Q)

The NPI-Q is an informant-based instrument that measures the presence and severity of 12 neuropsychiatric symptoms (e.g., anxiety, disinhibition, agitation/aggression). NPI-Q scores include Severity score (for patient) and Distress score (for caregiver). The severity scale has scores ranging from 1 to 3 points, and the scale for assessing caregiver distress has scores ranging from 0 to 5 points. Higher scores indicate more severity/distress. Total severity score is calculated as sum of severity scores for all 12 domains; and total distress score is calculated as sum of distress scores for all 12 domains.

In the MAD Period, the NPI-Q total severity score and total distress score (actual value, absolute change and percent change from baseline) will be summarized by treatment group and each post-baseline at Day 113, 169 and 253 visits using descriptive statistics. The absolute changes from baseline at each post-baseline visit will be compared between each ISIS 814907 treated analysis group and pooled placebo using the ANCOVA with baseline value as a covariate or Wilcoxon Rank Sum test, as appropriate.

In the LTE Period, the actual values, changes and percent changes will be summarized by analysis group and post-baseline visit at Day 449.

All NPI-Q collected scores will be presented in data listings for the MAD and MAD+LTE Periods.

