6.2.10.5 Functional Activities Questionnaire (FAQ)

The FAQ is a widely-used scale to assess activities of daily living in patients with mild AD (Brown et al. 2011; Marshall et al. 2011). It is a brief questionnaire in which the trial partner rates the patient's abilities in ten areas, such as keeping track of current events and preparing a balanced meal, on a scale of 0 (normal) to 3 (dependent). A score of 30 represents maximal dependence, and a score of 0 represents complete independence (Pfeffer et al. 1982).

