6.2.10.6 Neuropsychiatric Inventory – Questionnaire (NPI-Q)

The Neuropsychiatric Inventory (NPI) assesses behavioral disturbances occurring in dementia patients to evaluate a wide range of psychopathology and distinguish among different etiologies of dementia (Cummings 1997). The NPI-Questionnaire (NPI-Q) is a brief questionnaire form of the NPI intended to identify clinically significant neuropsychiatric disturbances and their associated impact on caregivers (Kaufer et al. 2000). It is completed by the test administrator after discussion with the trial partner about the presence/absence in the patient of 12 behaviors (e.g., anxiety, disinhibition, agitation/aggression) and, for each behavior that is present, its severity (scale of 1-3, with 3 being the most severe) and the associated caregiver distress (scale of 0-5, representing no distress through extreme distress).

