3.7.3.5 Clinical Dementia Rating (CDR) Scale

The CDR is a global scale used at Screening to categorize the severity of Alzheimer's type dementia. It is used to rate the patient's cognitive performance in 6 domains: memory,

orientation, judgment and problem solving, community affairs, home and hobbies, and personal care. Categorical scores for each domain are 0 (none), 0.5 (questionable), 1 (mild), 2 (moderate) and 3 (severe). A summed total score (CDR Sum of Boxes [CDR-SOB]) is produced, and a global score (using the same 5 grades of dementia) is derived. CDR are collected at Screening (all cohorts), Registration/Part 2 (Cohorts A and B only) and Day 449/Part 2 (all cohorts).

In the MAD period, the CDR-SOB at Screening will be summarized as baseline characteristics.

In the LTE and MAD+LTE Periods, CDR-SOB, global score and subdomain scores (actual value, absolute change and percent change from baseline) will be summarized by analysis group and each post-baseline visit at Registration visit (for Cohorts A and B only) and at Day 449 visit.

All CDR collected scores will be presented in data listings for the MAD and MAD+LTE Periods.

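### Percent change from baseline is planned for NPI-Q totals, MMSE domain scores and CDR subdomain scores; a zero baseline makes it undefined and drops patients in one direction only

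*Combined protocol and SAP*

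**What the plan says.** SAP 3.7.3 commits to percent change on four clinical instruments, each time beside the actual value and the absolute change:

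- NPI-Q (3.7.3.4), MAD Period: "the NPI-Q total severity score and total distress score (actual value, absolute change and percent change from baseline". For the LTE Period: "the actual values, changes and percent changes will be summarized by analysis group and post-baseline visit at Day 449".
- MMSE (3.7.3.3): "MMSE domain scores and total score (actual value, absolute change and percent change from baseline".
- CDR (3.7.3.5), LTE and MAD+LTE Periods: "CDR-SOB, global score and subdomain scores (actual value, absolute change and percent change from baseline".
- FAQ (3.7.3.1): "FAQ total score (actual value, absolute change and percent change from baseline".

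The scale descriptions allow zeros. In protocol 6.2.10.6 the NPI-Q records, "for each behavior that is present, its severity (scale of 1-3, with 3 being the most severe"; on the distress side, SAP 3.7.3.4 says "the scale for assessing caregiver distress has scores ranging from 0 to 5 points". For FAQ, protocol 6.2.10.5 says "a score of 0 represents complete independence". CDR boxes start at 0, and the MMSE visual construction domain is a single point.

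SAP 3.4.2 says only that missing values are not imputed. Protocol 10.6.4 makes percent change conditional on its being suitable. The SAP's clinical sections drop that condition and use similar wording only for the choice between ANCOVA and the Wilcoxon test.

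**The concern.** Percent change divides by the baseline value, so a zero baseline gives no result and the patient leaves that column. If zeros were incidental, this would be a footnote about a smaller n. Here a patient at the floor of a scale can move in one direction only, so leaving those patients out pushes the summary one way. Just above the floor the opposite problem arises: a one-point move on a denominator of 1 or 2 swamps the group mean.

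SAP 1.3.1 says the clinical evaluations serve to watch for unexpected deterioration. A column that cannot show a first symptom on NPI-Q, or a first impairment in a CDR box, suits that purpose poorly. Elsewhere the SAP is more careful. Section 3.7.1 models biomarkers as log ratios because percent change is not always normally distributed, and 3.7.2.1 summarizes brain volumes by absolute change without percent change.

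**Working it through.** The plan gives no figure to reproduce for this point. The checks are whether zeros can occur, what the formula then does, and how often a group would be affected.

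**1. Can the baseline be zero?**

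- *NPI-Q totals.* Severity is rated only for behaviors that are present, and distress starts at 0. A patient with no behaviors totals 0, provided an absent behavior counts as 0. SAP 3.7.3.4 does not say so: it gives severity as 1 to 3 and sums over all 12 domains.
- *MMSE domains.* The maxima in SAP 3.7.3.3 are orientation 10, memory 6, attention 5, language 8 and visual construction 1, in total 30. Entry requires a total of 20 to 27 (protocol 5.1.1). With one domain at 0, the highest possible total is 30 minus that domain's maximum: 20, 24, 25, 22 and 29 respectively. Each is at least 20, so any single domain can be 0 in an eligible patient.
- *CDR.* Entry requires a global score of 1, or 0.5 with a Memory score of 1. CDR global and CDR-SOB therefore cannot be 0 at MAD baseline, but individual boxes can. MMSE total cannot be 0 either.
- *FAQ total.* Zero is the floor. Entry requires probable AD dementia, so a zero is probably uncommon.

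**2. What does the formula give?** Percent change = 100 × (post − baseline) / baseline.

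| Score | Baseline → post | Absolute change | Percent change |
|---|---|---|---|
| NPI-Q or FAQ | 0 → 3 | +3 | undefined |
| NPI-Q or FAQ | 1 → 2 | +1 | +100% |
| NPI-Q or FAQ | 10 → 11 | +1 | +10% |
| MMSE drawing | 0 → 1 | +1 | undefined |
| MMSE drawing | 1 → 0 | −1 | −100% |
| CDR box | 0 → 0.5 | +0.5 | undefined |
| CDR box | 0.5 → 1 | +0.5 | +100% |
| CDR box | 1 → 0.5 | −0.5 | −50% |

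MMSE drawing can give only 0%, −100% or nothing, so its group mean can never exceed 0%. Equal and opposite moves on a CDR box do not cancel.

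**3. How often would a group be affected?** Cohorts of 8, 8, 12 and 16 at 3:1 give active groups of 6, 6, 9 and 12 and a pooled placebo group of 2 + 2 + 3 + 4 = 11. The share *q* of patients with a zero baseline is not in the documents, so I assume a range. P(at least one undefined value in a group of n) = 1 − (1 − q)^n.

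| Assumed q | n = 6 | n = 9 | n = 11 | n = 12 | Expected zeros in 44 |
|---|---|---|---|---|---|
| 5% | 0.26 | 0.37 | 0.43 | 0.46 | 2.2 |
| 10% | 0.47 | 0.61 | 0.69 | 0.72 | 4.4 |
| 20% | 0.74 | 0.87 | 0.91 | 0.93 | 8.8 |

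**4. Illustration with invented data**, a group of six on NPI-Q severity. Baselines are 0, 0, 1, 2, 5, 10 and post values 3, 2, 2, 1, 4, 8.

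- Absolute change, all six: (3 + 2 + 1 − 1 − 1 − 2) / 6 = +0.33.
- Absolute change, the four with a non-zero baseline: (1 − 1 − 1 − 2) / 4 = −0.75.
- Percent change, the same four: (100 − 50 − 20 − 20) / 4 = +2.5%.

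The percent-change mean leaves out the two patients who worsened most. It also has the opposite sign to the absolute change in the four it keeps.

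**The case against.** The strongest reply is that nothing depends on this column. Percent change is one of three descriptive measures. A patient with a zero baseline still appears in the actual values, the absolute change and the listings. The planned between-group comparisons for FAQ, MMSE and NPI-Q use absolute change, CDR has no test, and no stated decision rule uses percent change on these scales. SAP 3.1 lists the number of patients and the median among its standard statistics, so a reduced n should be visible. SAP section 1 also calls its methods flexible. All of this stands, and it keeps the point small.

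A reader might go further and infer that patients who newly develop symptoms vanish from safety monitoring. The documents do not support that: these patients leave one column, and protocol 10.1.3 describes monitoring of the individual patient. Nor are all CDR and MMSE scores affected, since entry criteria exclude a zero at MAD baseline for CDR global, CDR-SOB and MMSE total. For MMSE domains the lost information is improvement, not deterioration.

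What does not fall away is that the SAP, followed as written, produces a one-sided summary and has no rule for the case. A visible n shows that patients are missing, but not that they could have moved in only one direction.

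**Conclusion.** The point holds as a minor one. For NPI-Q totals, MMSE domain scores and CDR subdomain scores, the planned percent change is undefined at a baseline the documents allow, and the exclusion is directional. For FAQ total the same can happen, but distortion by low baselines is the likelier problem.

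That zeros are possible follows from the documents alone, except that for NPI-Q it assumes an absent behavior scores 0. How often they occur does not follow: the 5% to 20% range is an assumption, and the group of six is invented. The size of any bias in this trial therefore cannot be stated. The distortion is strongest on very short scales and at low baselines, and it fades for patients well above the floor. No planned test or trial conclusion is at risk.

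**What to change.** In SAP 3.7.3.3 to 3.7.3.5, delete percent change for NPI-Q total severity and distress, MMSE domain scores and CDR subdomain scores, and preferably for FAQ total in 3.7.3.1. Keep actual value and absolute change. Add, by analysis group and visit, the number of patients who move from zero at baseline to above zero. This reads as new symptoms or impairment on NPI-Q, FAQ and CDR boxes, and as improvement on MMSE domains. State in 3.7.3.4 that an absent NPI-Q behavior scores 0.

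If percent change is kept for any score that can be zero, report the number of patients contributing and the number excluded for a zero baseline.

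The cost is SAP wording and table shells: some columns go and one count is added. No new data are needed, and the planned ANCOVA and Wilcoxon comparisons do not change.
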